Table 3:	Schedule of Activities.....	10
Table 4:	Objectives and Endpoints	13
Table 5:	Study Treatment Information	16
Table 6:	Required Laboratory Analytes.....	23

LIST OF FIGURES

Figure 1: Study Design Schema	9
-------------------------------------	---

LIST OF ABBREVIATIONS

Abbreviations and Special Terms	Definition
AE	adverse event
CFR	Code of Federal Regulations
COVID-19	coronavirus disease 2019
CTCAE	Common Terminology Criteria for Adverse Events
ECG	electrocardiogram
eCRF	electronic case report form
EDC	electronic data capture
EOT	end of treatment
FDA	Food and Drug Administration
FGFR	fibroblast growth factor receptor
GCP	Good Clinical Practice
GDPR	General Data Protection Regulation
HIPAA	Health Insurance Portability and Accountability Act of 1996
IB	Investigator's Brochure
ICF	informed consent form
ICH	International Council for Harmonisation of Technical Requirements for Pharmaceuticals for Human Use
ID	identification
IEC	independent ethics committee
IRB	institutional review board
IRT	interactive response technology
IV	intravenous
MedDRA	Medical Dictionary for Regulatory Activities
PD-1	programmed death 1
RSI	reference safety information
SAE	serious adverse event
SARS-CoV-2	severe acute respiratory syndrome coronavirus 2
SOP	standard operating procedure
study treatment	refers to pemigatinib monotherapy or combination therapy with pemigatinib
TEAE	treatment-emergent adverse event

1. PROTOCOL SUMMARY

Protocol Title:

An Open-Label, Multicenter, Rollover Study to Provide Continued Treatment for Participants With Advanced Malignancies Previously Enrolled in Studies of Pemigatinib

Protocol Number: INCB 54828-801

Objectives and Endpoints:

[Table 1](#) presents the primary and major/key secondary objectives and endpoints.

Table 1: Objectives and Endpoints

Objectives	Endpoints
To evaluate the long-term safety and tolerability of pemigatinib.	Frequency and nature of AEs and SAEs as assessed by CTCAE v5.0.

Overall Design:

[Table 2](#) presents the key study design elements. Further study details are presented after the table.

Table 2: Key Study Design Elements

Study Phase	Phase 2
Clinical Indication	Treatment of patients with advanced malignancies
Population	Male and female participants at least 18 years of age who are actively receiving treatment with pemigatinib under a parent protocol and receiving clinical benefit and who do not have access to pemigatinib outside of a clinical trial.
Number of Participants	Approximately 20 participants will be enrolled from prior pemigatinib studies.
Study Design	Single-arm, open-label, rollover
Estimated Duration of Study Participation	Participants will be allowed to continue to receive pemigatinib until they meet the criteria noted in Section 7.1 .
Data Safety Monitoring Board/Data Monitoring Committee	No
Coordinating Principal Investigator	Not applicable

[Figure 1](#) presents the study design schema, and [Table 3](#) presents the schedule of activities.

Figure 1: Study Design Schema

[figure not shown]

Table 3: Schedule of Activities

	Day 1 of Each Cycle	EOT	Safety Follow-Up	Comments
Informed consent	X*			*Only on Day 1 of rollover protocol.
Demography	X*			*Only on Day 1 of rollover protocol.
Contact IRT	X	X		
Dispense pemigatinib	X			
Collect remaining pemigatinib	X*	X		*Starting Cycle 2 Day 1.
Administer pembrolizumab (only for participants receiving under parent protocol)	X*			*Administer 200 mg IV once every 3 weeks on Day 1 of a 21-day cycle (3 weeks).
Administer INCMGA00012 (only for participants receiving under parent protocol)	X*			*Administer 500 mg IV once every 4 weeks on Day 1 of a 28-day cycle (4 weeks).
AE assessments	X	X	X	
12-lead ECG	X*	X		*Every 6 cycles starting from last ECG on parent study.
Ophthalmologic examinations	X*			*Every 3 cycles starting from last eye examination on parent study.
Serum chemistry	X	X		
Hematology	X*	X		*Every 3 cycles starting from last blood draw on parent study.
Disease assessment	X*			*Assess per standard of care guidelines; only report date of progression.
Urine pregnancy test	X*	X	X	*If urine test is positive, perform serum test to confirm.

2. INTRODUCTION

2.1. Background

The rollover protocol is intended for participants currently enrolled in Incyte-sponsored studies who are continuing to receive clinical benefit from treatment with pemigatinib (monotherapy or in combination). Continued, uninterrupted treatment will be provided under this single protocol. The population for the rollover study should be consistent with the populations defined in the parent studies. The primary eligibility criterion for a participant to enter the rollover protocol is participation in an Incyte-sponsored study with pemigatinib as monotherapy or combination therapy and receiving ongoing treatment with pemigatinib. Disease assessments should be performed per standard of care, with date of progression reported and safety data collected.

Participants who have enrolled in a prior study with pemigatinib as monotherapy or combination therapy and are assessed by the investigator to continue to benefit from ongoing treatment and who are unable to access pemigatinib outside of a clinical study will be eligible.

2.2. Study Rationale

2.2.1. Scientific Rationale for Study Design

Pemigatinib is an inhibitor of the FGFR family of receptor tyrosine kinases; aberrant signaling through FGFR resulting from gene amplification or mutation, chromosomal translocation, and ligand-dependent activation of the receptors has been demonstrated in multiple types of human cancers. Fibroblast growth factor receptor signaling contributes to the development of malignancies by promoting tumor cell proliferation, survival, migration, and angiogenesis. Refer to the [pemigatinib IB](#) for additional background information on pemigatinib.

2.2.2. Justification for Dose of Pemigatinib

Participants will continue to receive uninterrupted treatment with pemigatinib as monotherapy or combination therapy during the transition to this protocol. The participants will continue to be treated with pemigatinib monotherapy or combination therapy at the dose and schedule (intermittent or continuous) that the participant is receiving under the parent protocol. For example, if the participant's dose had been reduced to 9 mg once daily continuous dosing on the parent protocol, the participant will rollover into this protocol at that dose and regimen.

2.2.3. Justification for Dose of Pembrolizumab and INCMGA00012

Participants will continue to receive uninterrupted treatment with pemigatinib in combination with either pembrolizumab or INCMGA00012 as per the parent protocol during the transition to this protocol. The participants will continue to be treated with pembrolizumab or INCMGA00012 at the dose and schedule that the participant is receiving under the parent protocol. No changes to the dose or regimen of the combination (either compound) is allowed during the transition to the rollover study.

2.3. Benefit/Risk Assessment

More detailed information about the known and expected benefits and risks and reasonably expected AEs of pemigatinib, INCMGA00012, and pembrolizumab may be found in the [pemigatinib IB](#), [INCMGA00012 IB](#), and [KEYTRUDA® \(pembrolizumab\) prescribing information](#), respectively.

2.3.1. Benefit/Risk Assessment During the COVID-19 Pandemic

Participants to be enrolled into this study have recurrent advanced or metastatic endometrial cancer and may be at higher risk for complications if they contract COVID-19. In this Phase 2 study population, standard of care therapy options for advanced or metastatic endometrial cancer that progressed on or following platinum-based chemotherapy are limited. A European Society for Medical Oncology multidisciplinary panel highlighted the importance of clinical cancer research to find better therapeutic options for participants even during the pandemic, including potential investigational therapies similar to immunotherapy with a known survival benefit ([Curigliano et al 2020](#)). Preliminary data released based on real-world data indicate that the use of immunotherapy either alone or in combination with chemotherapy does not appear to increase the risk of hospitalization in patients with COVID-19 infection ([Horn et al 2020](#)) or cause an increased risk of mortality ([Lee et al 2020](#)). The effects of immune checkpoint inhibitors on SARS-CoV-2 infection are currently unknown. However, at early stages of SARS-CoV-2 infection, CD8+ T-cell exhaustion and PD-1 upregulation have been observed ([Riva et al 2020](#), [Zheng et al 2020](#)). Those findings suggest that immune checkpoint inhibitors may ameliorate the early phase of COVID-19 through the reactivation of T cells expressing PD-1 ([Maio et al 2020](#)). Conversely, potential risks of cytokine release syndrome, pneumonitis, or myocarditis related to immune checkpoint inhibitor therapy may represent a clinical issue and impact a course of COVID-19 ([Maio et al 2020](#), [Sullivan et al 2020](#)). Considering the critical medical need for alternative therapies in the setting of recurrent advanced/metastatic endometrial cancer and the importance of continuing clinical cancer research even during the pandemic and taking into account the lack of conclusive clinical data on the impact of immune checkpoint inhibitor therapy on the course of COVID-19, the sponsor is implementing additional guidance for participation in this study in the context of the COVID-19 pandemic and study treatment management in the event of SARS-CoV-2 infection (see [Appendix C](#)).

During the COVID-19 pandemic, additional risks to participants exist either related to going to a health care facility or as a result of study-related activities. The investigators need to carefully assess both the benefit/risk and the medical data (eg, performance status, past medical history, comorbidities) available at screening to determine if it is in the best interest of the potential participant to enroll and participate in the study. In addition, country-specific requirements will be followed with regard to COVID-19 testing, as specified in [Appendix C](#). Investigators will follow up with repeated tests during the study as per medical judgment and/or local practices as well as follow up with enrolled participants who may be newly suspected of being exposed to SARS-CoV-2, have symptoms of COVID-19, or demonstrate recovery from COVID-19.

Participants will be monitored with safety procedures as described in Section 8 and with additional safety assessments as per standard of care. Additional information regarding the flexibility of assessments/visits scheduling, where possible and warranted, and a strategy for participant management during the dynamic pandemic, as applicable, are described in [Appendix C](#).

3. OBJECTIVES AND ENDPOINTS

[Table 4](#) presents the objectives and endpoints.

Table 4: Objectives and Endpoints

Objectives	Endpoints
To evaluate the long-term safety and tolerability of pemigatinib.	Frequency and nature of AEs and SAEs as assessed by CTCAE v5.0.

4. STUDY DESIGN

4.1. Overall Design

This rollover protocol allows study participants from multiple protocols who are receiving clinical benefit to continue to be treated during the completion of the parent study (also referred to as parent protocol). The population for the rollover study should be consistent with the population defined in each parent protocol. The primary eligibility criterion for a participant to enter the rollover protocol is participation in an Incyte-sponsored study (parent protocol) with pemigatinib as monotherapy or combination therapy and receiving ongoing treatment with pemigatinib.

Participants who have enrolled in a prior study (parent protocol) with pemigatinib as monotherapy or combination therapy and are assessed by the investigator to continue to benefit from ongoing treatment and who cannot access pemigatinib outside of a clinical trial will be eligible.

Disease assessments will be performed per standard of care, with date of progression reported and safety data collected.

Once a participant has rolled over into this protocol from a parent protocol, the database for the parent protocol will be closed and locked, and the parent protocol study will be considered completed and closed. However, the participant in the rollover protocol will still be treated as per the plan outlined in the parent protocol. The list of parent protocols is provided in [Appendix B](#).

4.2. Overall Study Duration

The study begins when the first participant signs the study ICF. The end of the study is defined as the date of the last visit of the last participant in the study. It is estimated that an individual will participate for approximately 12 months.

The study is considered completed when the last participant's last visit has occurred.

4.3. Study Termination

The investigator retains the right to terminate study participation at any time, according to the terms specified in the study contract. The investigator is to notify the IRB/IEC of the study's completion or early termination in writing, send a copy of the notification to the sponsor or sponsor's designee, and retain 1 copy for the site study regulatory file.

5. STUDY POPULATION

Deviations from eligibility criteria are not allowed because they can potentially jeopardize the scientific integrity of the study, regulatory acceptability, and/or participant safety. Therefore, adherence to the criteria as specified in the parent protocol as well as this protocol is essential. Prospective approval of protocol deviations to recruitment and enrollment criteria, also known as protocol waivers or exemptions, are not permitted.

5.1. Inclusion Criteria

Participants are eligible to be included in the study only if all of the following criteria apply:

1. Currently enrolled and receiving treatment in an Incyte-sponsored clinical study (parent protocol) of pemigatinib as monotherapy or combination therapy.
2. Currently benefiting from and tolerating treatment with pemigatinib, as determined by the investigator.
3. Demonstrated compliance, as assessed by the investigator, with the parent protocol requirements.
4. Willingness and ability to comply with scheduled visits, treatment plans, and any other study procedures.
5. Currently have no evidence of progressive disease, as determined by the investigator, following treatment with pemigatinib as monotherapy or combination therapy.
6. Willingness to avoid pregnancy or fathering children based on the criteria below.
 - a. Male participants must agree to take appropriate precautions to avoid fathering children (with at least 99% certainty) from signing of the ICF through 90 days after the last dose of pemigatinib and 6 months after the last dose of gemcitabine and/or cisplatin and must refrain from donating sperm during this period. Permitted methods that are at least 99% effective in preventing pregnancy (see [Appendix A](#)) should be communicated to the participants and their understanding confirmed. NOTE: Men being treated with gemcitabine must be advised to seek further advice regarding cryoconservation of sperm before treatment because of the possibility of infertility due to therapy with gemcitabine.
 - b. Women of nonchildbearing potential (ie, surgically sterile with a hysterectomy and/or bilateral oophorectomy OR ≥ 12 months of amenorrhea) are eligible.
 - c. Women of childbearing potential must have a negative serum pregnancy test at signing of the ICF and before the first dose on Day 1 and must agree to take appropriate precautions to avoid pregnancy (with at least 99% certainty) from signing of the ICF through safety follow-up (30-35 days after the last dose of pemigatinib) and through 6 months after the last dose of gemcitabine and/or cisplatin. Permitted methods that are at least 99% effective in preventing pregnancy (see [Appendix A](#)) should be communicated to the participants and their understanding confirmed.
7. Written informed consent obtained prior to enrolling in the rollover study. If consent cannot be expressed in writing, it must be formally documented and witnessed, ideally via an independent trusted witness.

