8.3.2.1. Pregnancy Testing

A urine pregnancy test will be required for all women of childbearing potential on Day 1 of this study and at the EOT and safety follow-up visits. Urine pregnancy tests will be performed locally as outlined in [Table 3](#), as medically indicated (eg, in case of loss of menstrual cycle, when pregnancy is suspected), or per country-specific requirement (note that country-required urine pregnancy testing will be outlined and communicated to investigational sites under separate cover). If a urine pregnancy test is positive, the result should be confirmed with a serum pregnancy test.

If the serum pregnancy test is negative after a urine test was positive, the investigator will assess the potential benefit/risk to the participant and determine whether it is in the participant's best interest to resume study treatment and continue participation in the study.

If a pregnancy is confirmed by a serum pregnancy test, see Section [9.6](#) for reporting requirements.

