APPENDIX A. INFORMATION REGARDING EFFECTIVENESS OF CONTRACEPTIVE METHODS AND DEFINITIONS

Definitions
WOCBP: A woman who is considered fertile following menarche and until becoming postmenopausal unless permanently sterile (see below). Women in the following categories are not considered WOCBP: 
• Premenarchal• Premenopausal with 1 of the following:^a
– Documented hysterectomy– Documented bilateral salpingectomy– Documented bilateral oophorectomy• Postmenopausal
– A postmenopausal state is defined as no menses for 12 months without an alternative medical cause.
○ A high FSH level in the postmenopausal range may be used to confirm a postmenopausal state in women not using hormonal contraception or HRT. However, in the absence of 12 months of amenorrhea, confirmation with 2 FSH measurements in the postmenopausal range is required.– Females on HRT and whose menopausal status is in doubt will be required to use 1 of the nonhormonal, highly effective contraception methods if they wish to continue their HRT during the study. Otherwise, they must discontinue HRT to allow confirmation of postmenopausal status before study enrollment.
For male participants of reproductive potential ^b
The following methods during the Protocol-defined timeframe in Section 5.1 are highly effective: 
• Use of a male condom plus partner use of an additional contraceptive method when having penile-vaginal intercourse with a woman of childbearing potential who is not currently pregnant.• Vasectomy with medical assessment of the surgical success (verified by site personnel's review of the participant's medical records)• Sexual abstinence^c
– Abstinence from penile-vaginal intercourse
The following are not acceptable methods of contraception: 
• Periodic abstinence (calendar, symptothermal, post ovulation methods), withdrawal (coitus interruptus), spermicides only, and lactational amenorrhea method.• Male condom with cap, diaphragm, or sponge with spermicide.• Male and female condom used together.
Note: Men with a pregnant or breastfeeding partner must agree to remain abstinent from penile-vaginal intercourse or use a male condom during each episode of penile penetration.

For female participants who are WOCBP

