The following methods during the Protocol-defined timeframe in Section 5.1 that can achieve a failure rate of less than 1% per year when used consistently and correctly are considered as highly effective birth control methods:

- Combined (estrogen and progestogen containing) hormonal contraception associated with inhibition of ovulation^d
 - oral
 - intravaginal
 - transdermal
- Progestogen-only hormonal contraception associated with inhibition of ovulation^d
 - oral
 - injectable
 - implantable^e
- Intrauterine device^e
- Intrauterine hormone-releasing system^e
- Bilateral tubal occlusion^e
- Vasectomized partner^{e,f}
- Sexual abstinence^c

FSH = follicle-stimulating hormone; HRT = hormone replacement therapy.

^a Documentation can come from the site personnel's review of the participant's medical records, medical examination, or medical history interview.

^b If the male participant has a partner with childbearing potential, the partner should also use contraceptives.

^c In the context of this guidance, sexual abstinence is considered a highly effective method only if defined as refraining from heterosexual intercourse during the entire period of risk associated with the study treatments. The reliability of sexual abstinence needs to be evaluated in relation to the duration of the clinical study and the preferred and usual lifestyle of the participant.

^d Hormonal contraception may be susceptible to interaction with the investigational medicinal product, which may reduce the efficacy of the contraception method. In this case, 2 methods of contraception should be used.

^e Contraception methods that in the context of this guidance are considered to have low user dependency.

^f Vasectomized partner is a highly effective method of avoiding pregnancy provided that partner is the sole sexual partner of the WOCBP study participant and that the vasectomized partner has received medical assessment of the surgical success.

Source: [Clinical Trials Facilitation and Coordination Group 2020](#).

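### Inclusion criterion 6b accepts 12 months of amenorrhea from any cause as nonchildbearing potential, which conflicts with the stricter definition in Appendix A

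*Protocol*

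**What the plan says.** Criterion 6b in Protocol Section 5.1 carries its own closed definition: "Women of nonchildbearing potential (ie, surgically sterile with a hysterectomy and/or bilateral oophorectomy OR ≥ 12 months of amenorrhea) are eligible". It sets no condition on why menstruation stopped and does not point to Appendix A.

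Appendix A contains the protocol's only definition of a woman of childbearing potential: "A woman who is considered fertile following menarche and until becoming postmenopausal unless permanently sterile". It then narrows the menopause route: "A postmenopausal state is defined as no menses for 12 months without an alternative medical cause". It adds a hormone-testing route for women short of the 12 months ("However, in the absence of 12 months of amenorrhea, confirmation with 2 FSH measurements in the postmenopausal range is required") and a rule for hormone replacement therapy ("Females on HRT and whose menopausal status is in doubt will be required to use 1 of the nonhormonal, highly effective contraception methods", or else stop the therapy so that status can be confirmed). It also lists bilateral salpingectomy among the surgical routes.

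Two sets of duties depend on the classification. Criterion 6c says "Women of childbearing potential must have a negative serum pregnancy test at signing of the ICF and before the first dose on Day 1" and adds a contraception agreement that runs through safety follow-up. Section 8.3.2.1 requires a urine test for "all women of childbearing potential on Day 1 of this study and at the EOT and safety follow-up visits".

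Within Section 5.1, Appendix A is cited in 6a and 6c only, both times for contraceptive methods. The appendix refers back to Section 5.1 only for the period over which those methods are needed ("The following methods during the Protocol-defined timeframe in Section 5.1 that can achieve a failure rate of less than 1% per year").

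**The concern.** The same woman can be nonchildbearing under the eligibility criterion and of childbearing potential under the appendix. She is not surgically sterile and has had no menses for 12 months or more, and her amenorrhea has a medical explanation. Earlier chemotherapy would be one example; that is my illustration, not one from the documents.

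A site that classifies her by 6b is following the criterion as written. Section 5 insists on adherence to the criteria and permits no waivers, so a monitor checking 6b alone would have nothing to query.

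At stake is an undetected or unprevented pregnancy during treatment. The protocol treats that seriously: pregnancy is a mandatory reason for stopping treatment in Section 7.1.1, and Section 9.6 requires immediate interruption in female participants.

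**Working it through.** There is no figure in the plan to reproduce. The check sets the two definitions side by side and then counts what depends on them.

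**Classification**

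| Woman | Criterion 6b | Appendix A | Effect of following 6b |
|---|---|---|---|
| Uterus or both ovaries removed | Nonchildbearing | Nonchildbearing | None |
| 12 months of amenorrhea, no other cause | Nonchildbearing | Nonchildbearing | None |
| 12 months of amenorrhea with a medical cause, not sterilised | Nonchildbearing | Childbearing potential | Safeguards lost |
| Both fallopian tubes removed | Not listed, so falls to 6c | Nonchildbearing | 6b stricter |
| Under 12 months of amenorrhea, two postmenopausal FSH values | Not listed, so falls to 6c | Can be confirmed postmenopausal | 6b stricter |
| On hormone replacement, 12 months of amenorrhea, status in doubt | Nonchildbearing | Nonhormonal contraception, or stop the therapy | Appendix A rule still binds, but 6b does not point to it |

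The 12-month threshold is the same in both places. The safety difference is the condition on cause, in the third row.

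**Scheduled tests for the woman in the third row, not yet dosed**

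- Serum tests, from 6c: at consent and before the first dose. That is 2, or 1 if both fall on the same day.
- Urine tests, from Section 8.3.2.1: Day 1, end of treatment and safety follow-up. That is 3.
- Total if Appendix A is applied: 1 + 3 = 4, or 2 + 3 = 5, plus the contraception agreement.
- Total if 6b is read literally: 0 scheduled tests and no contraception agreement. Testing on medical indication remains.
- If she is already past Day 1 when reclassified: 3 − 1 = 2 scheduled urine tests remain.

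These counts follow the text of Section 8.3.2.1. Table 3 marks the urine test under Day 1 of every cycle. If that column governs, a woman who starts C cycles has C + 2 urine tests instead of 3. The two agree only when C = 1, so 4 to 5 is a lower figure. That mismatch is a separate matter.

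**Which definition prevails**

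No text in the protocol or SAP ranks 6b against Appendix A. The parent-protocol criteria also apply (Section 5 and exclusion 3), but they are not reproduced, so they cannot be assumed to contain the condition on cause.

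**The case against.** The best reply is that the protocol already contains the right rule. Appendix A names definitions in its title and opens with this one. Criterion 6c, directly after 6b, sends the site there. Read as a whole, the protocol lacks only a cross-reference, and harm requires a site to apply 6b and overlook an appendix it has to open anyway. Every participant has also been enrolled and treated under a parent protocol whose criteria she must still meet. Exclusion 4 bars women who are pregnant or expect to conceive. The stem of criterion 6 asks all participants to be willing to avoid pregnancy. Section 8.3.2.1 allows testing whenever it is medically indicated.

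Most of this stands, and it limits the size of the point. It does not remove the conflict. Criterion 6c cites the appendix for methods, and a woman already classed under 6b never reaches 6c. The stem of criterion 6 refers back to the sub-items. Exclusion 4 depends on knowing about a pregnancy, and literal 6b removes the scheduled tests that would reveal it. Loss of menses, one of the testing triggers in Section 8.3.2.1, is a poor signal in a woman who already has none.

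Three stronger readings are tempting and are not supported:

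- A reader might infer that women on hormone replacement therapy with doubtful status lose their protection. The Appendix A requirement is worded to stand alone, and 6b does not cancel it; it is merely hard to find from 6b.
- A reader might infer that the missing salpingectomy and FSH routes are further safety gaps. They work the other way: those women fall to 6c and are tested.
- A reader might infer that participants have in fact been misclassified. The documents do not show that, and the outcome depends on parent criteria that are not shown.

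**Conclusion.** Criterion 6b is wrong as written. It is an internal inconsistency that bears on participant safety and should be corrected. Confidence is high for the wording conflict and much lower for any practical consequence.

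For one affected woman not yet dosed, the difference is 4 to 5 scheduled tests and a contraception agreement against none of these under this protocol. This assumes that the site reads 6b literally, that Section 8.3.2.1 rather than the Table 3 cycle column sets the urine-test schedule, and that the parent protocol does not already impose the stricter definition.

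The number of such women among approximately 20 participants of both sexes is not given and may be zero. Enrolment status is not stated either, so the benefit for future entrants is unknown. The adverse event endpoint and the planned summaries are unaffected.

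**What to change.** Replace the parenthesis in 6b with *as defined in Appendix A*. In 6c, the Table 3 urine-test row (which names no population at present) and Section 8.3.2.1, write *women of childbearing potential as defined in Appendix A*. Adding only the condition on cause to 6b would close the safety gap but leave the salpingectomy, FSH and hormone-replacement differences in place; one cross-reference settles all of them using the sponsor's own definition.

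The cost is a wording amendment. Section 11.1 requires Health Authority and IRB/IEC approval of amendments, so it is best carried with the next one rather than alone.

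A reclassified woman not yet dosed takes on the 4 to 5 tests; one already dosed takes on the 2 remaining urine tests. Both figures rise if the Table 3 cycle column governs. Either woman also takes on contraception through safety follow-up, for which Appendix A accepts abstinence. In the other direction, women with bilateral salpingectomy, or with postmenopausal status confirmed by two FSH values, would no longer need the testing and contraception that 6c now imposes on them. No analysis has to be revised.
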